5.0 Patient Eligibility

Inclusion Criteria:

Patients will be eligible for inclusion in the study if they meet all of the following criteria:

1. Patients age > 18 years at the time of signing informed consent. Understand and voluntarily sign an informed consent.

2. Patients with CLL or SLL with active disease.
3. Prior treatment with purine analog based chemotherapy or chemoimmunotherapy.
4. Platelet count $\geq 30,000 \text{ mm}^3$
5. ECOG/WHO performance status of 0-2
6. Adequate renal function indicated by creatinine clearance $> 30 \text{ ml/min}$ (calculated by 24 hours urine collection) or a GFR $> 30 \text{ ml/min}$ estimated using the Cockcroft-Gault equation. Adequate hepatic function indicated as total bilirubin less or equal to 2 mg/dl and ALT less or equal to two times the upper limit of normal.
7. Disease free of prior malignancies for 3 years with exception of currently treated basal cell, squamous cell carcinoma of the skin, or carcinoma "in situ" of the cervix or breast. Patients with malignancies with indolent behavior such as prostate cancer treated with radiation or surgery can be enrolled in the study as long as they have a reasonable expectation to have been cured with the treatment modality received.
8. Females of childbearing potential (FCBP)[†] must have a negative serum or urine pregnancy test with a sensitivity of at least 50 mIU/mL within 10 – 14 days prior to starting lenalidomide and again within 24 hours prior to prescribing lenalidomide (prescriptions must be filled within 7 days) and prior to first administration of ofatumumab and must either commit to continued abstinence from heterosexual intercourse or begin TWO acceptable methods of birth control, one highly effective method and one additional effective method AT THE SAME TIME, at least 28 days before she starts taking lenalidomide and continue it for 6 months after therapy has been completed. FCBP must also agree to ongoing pregnancy testing. Men must agree to use a latex condom during sexual contact with a FCBP even if they have had a successful vasectomy. All study participants must be registered into the mandatory RevAssist® program, and be willing and able to comply with the requirements of RevAssist®. See Appendix: Risks of Fetal Exposure, Pregnancy Testing Guidelines and Acceptable Birth Control Methods.

Exclusion Criteria:

[†] A female of childbearing potential is a sexually mature woman who: 1) has not undergone a hysterectomy or bilateral oophorectomy; or 2) has not been naturally postmenopausal for at least 24 consecutive months (i.e., has had menses at any time in the preceding 24 consecutive months).

1. Known sensitivity to lenalidomide, other thalidomide derivatives or ofatumumab.
2. Documented prolymphocytic leukemia (prolymphocytes more than 55% in the blood).
3. Known positivity for HIV or active hepatitis B or C.

Known positivity for HIV or active hepatitis B or C. Positive serology for hepatitis B (HB) defined as a positive test for HBsAg. In addition, if negative for HBsAg but HBcAb positive regardless of HbsAb status, a HB DNA test will be performed and if positive the subject will be excluded.

4. Pregnant or breast feeding females. Women of childbearing potential must have a negative pregnancy test at screening. Male subjects unable or unwilling to use adequate contraception methods from study start to one year after the last dose of protocol therapy.
5. Chronic or current infectious disease requiring systemic antibiotics, antifungal, or antiviral treatment such as, but not limited to, chronic renal infection, chronic chest infection with bronchiectasis and tuberculosis. History of tuberculosis treated within the last five years or recent exposure to tuberculosis.
6. Any serious medical condition, laboratory abnormality, or psychiatric illness that places the subject at unacceptable risk if he/she were to participate in the study.
7. Patients with a recent history of deep vein thrombosis (DVT) or pulmonary embolus (PE), in the six months prior to enrollment are not eligible for this study.
8. Treatment with any known non-marketed drug substance or experimental therapy within 5 terminal half lives or 4 weeks prior to enrollment, whichever is longer, or currently participating in any other interventional clinical study
9. Prior treatment with other monoclonal antibodies within 4 weeks prior to enrollment.
10. Subjects meeting any of the following criteria must not be enrolled on study: Positive serology for Hepatitis B (HB) defined as a positive test for HBsAg. In addition, if negative for HBsAg but HBcAb positive (regardless of HBsAb status), a HB DNA test will be performed and if positive, the subject will be excluded.

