4.0 Treatment Plan

The administration of ofatumumab will be four weekly IV infusions at the dose of 300mg week 1, 1,000 mg week 2, 3 and 4, then monthly during months 2-6 and once every two months during months 7-24 (even months: 8,10,12 etc.). Lenalidomide will be given at the dose of 10mg daily. Lenalidomide will be started on day 9 – the day after the second infusion of ofatumumab and will be continued daily. Treatment duration will be 24 cycles and it will be possible to continue lenalidomide beyond 24 cycles if there is a significant benefit such as an ongoing PR or CR. Response will be evaluated after three, six, twelve, eighteen and twenty-four cycles. Only enough lenalidomide for 28 days of therapy will be supplied to the patient each cycle. Each cycle consists of 28 days. Patients with baseline creatinine clearance or calculated GFR ≥ 30 ml/min but < 50 ml/min will begin treatment at Dose Level – 1 (lenalidomide 5mg daily). These patients may be escalated to lenalidomide 10mg daily on Day 29 or later at physician discretion based on tolerability. Dose reduction steps will follow in accordance with Table 4 taken from their current dose.

Drug Dispensing Requirements

Lenalidomide:

Lenalidomide (Revlimid®) will be provided to research subjects for the duration of their participation in this trial at no charge to them or their insurance providers. Lenalidomide will be provided in accordance with the RevAssist® program of Celgene Corporation. Per standard RevAssist® requirements all physicians who prescribe lenalidomide for research subjects enrolled into this trial, and all research subjects enrolled into this trial, must be registered in and must comply with all requirements of the RevAssist® program. Prescriptions must be filled within 7 days. Only enough lenalidomide for one cycle of therapy will be supplied to the patient each cycle.

Lenalidomide capsules should be swallowed whole, and should not be broken, chewed or opened.

If a dose of lenalidomide is missed, it should be taken as soon as possible on the same day. If it is missed for the entire day, it should not be made up.

Patients who take more than the prescribed dose of lenalidomide should be instructed to seek emergency medical care if needed and contact study staff immediately.

Labeling and Lenalidomide Distribution

Lenalidomide will be shipped directly to patients via a specialty, Registered Pharmacy. Bottles will contain a sufficient number of capsules for one cycle of dosing.

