Once treatment has been completed or discontinued, liver function test (ALT, AST, alkaline phosphatase and bilirubin) will be performed 6 months (\pm 28 days) after the last dose of ofatumumab has been administered unless patients have received subsequent treatment for their CLL. Correlative laboratory studies and Quality of Life questionnaire (Appendix E) are optional and if the patient agrees they will be collected at baseline, at the end of cycles 3, 7, 13, 19, 23 and every 6 cycles after that (\pm 14 days).

You will be required to use TWO reliable forms of birth control, one highly effective method and one additional effective method at the same time or

practice complete abstinence from heterosexual intercourse during the following time periods related to this study: 1) for at least 28 days before starting lenalidomide; 2) while participating in this study; and 3) for at least 28 days after discontinuation from the study. The following are the acceptable birth control methods:

Highly Effective Methods	Additional Effective Methods
Intrauterine device (IUD)	Latex condom
Hormonal (birth control pills, injections, implants)	Diaphragm
Tubal ligation	Cervical Cap
Partner's vasectomy	

Females must not breastfeed a baby while participating in this study and for at least 28 days after you have been discontinued from the study.

Females of childbearing potential with regular or no menstrual cycles must agree to have pregnancy tests weekly for the first 28 days of study participation and then every 28 days while on study, at study discontinuation, and at day 28 following discontinuation from the study. If menstrual cycles are irregular, the pregnancy testing must occur weekly for the first 28 days and then every 14 days while on study, at study discontinuation, and at days 14 and 28 following discontinuation from the study.

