The MDACC "Internal SAE Report Form for Prompt Reporting" will be used for reporting to ORERM.

Serious adverse events will be captured from the time the patient signs consent until 30 days after the last dose of lenalidomide and for a minimum of 5 half lives (6 months) after the last dose of ofatumumab. If a subject does start other therapy, then SAEs will no longer be required to be reported.

Serious adverse events must be followed until clinical recovery is complete and laboratory tests have returned to baseline, progression of the event has stabilized, or there has been acceptable resolution of the event.

Additionally, any serious adverse events that occur after the 30 day time period that are related to the study treatment must be reported to ORERM. This may include the development of a secondary malignancy.

Reporting to FDA:

Serious adverse events will be forwarded to FDA by the IND Sponsor (Safety Project Manager ORERM) according to 21 CFR 312.32.

It is the responsibility of the PI and the research team to ensure serious adverse events are reported according to the Code of Federal Regulations, Good Clinical Practices, the protocol guidelines, the sponsor's guidelines, and Institutional Review Board policy.

NOTE: Instructions concerning procedures and reporting for pregnancies below.

Pregnancies

Pregnancy of a female subject or the female partner of a male subject occurring while the subject is on lenalidomide and ofatumumab or within 4 weeks after the

subject's last dose of lenalidomide or ofatumumab are considered expedited reportable events. If the subject is on lenalidomide, it is to be discontinued immediately and the subject is to be instructed to return any unused portion of lenalidomide to the Investigator. The pregnancy must be reported by the investigator to MDACC IRB and ORERM AND to Celgene Corporation Worldwide Drug Safety Surveillance (WWDSS) and to GSK within 24 hours of the Investigator's knowledge of the pregnancy by phone and facsimile using the SAE Form.

The Investigator will follow the subject until completion of the pregnancy, and must notify Celgene Corporation Worldwide Drug Safety Surveillance (WWDSS) of the outcome as specified below. The Investigator will provide this information as a follow-up to the initial SAE.

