If the outcome of the pregnancy meets the criteria for immediate classification as a SAE (i.e., spontaneous abortion [any congenital anomaly detected in an aborted fetus is to be documented], stillbirth, neonatal death, or congenital anomaly), the Investigator should follow the procedures for reporting SAEs (i.e., report the event to Celgene Corporation Worldwide Drug Safety Surveillance (WWDSS) by facsimile within 24 hours of the Investigator's knowledge of the event) and report the event to MDACC IRB and ORERM.

Any suspected fetal exposure to lenalidomide must be reported to Celgene, GSK, MDACC IRB AND ORERM within 24 hours of being made aware of the event. The patient should be referred to an obstetrician/gynecologist experienced in reproductive toxicity for further evaluation and counseling.

All neonatal deaths that occur within 30 days of birth should be reported, without regard to causality, as SAEs. In addition, any infant death after 30 days that the Investigator suspects is related to the in utero exposure to lenalidomide should also be reported.

In the case of a live "normal" birth, Celgene Corporation Worldwide Drug Safety Surveillance (WWDSS), GSK, MDACC IRB AND ORERM should be advised as soon as the information is available.

Drug Safety Contact Information:

Celgene Corporation
Worldwide Drug Safety Surveillance (WWDSS)
[name]
[name]

Toll Free: [contact]

[contact]
[contact]
e-mail: [contact]

GlaxoSmithKline
[name]
[name]
[contact]
E-mail: [contact]

Investigator Reporting Responsibilities

The conduct of the study will comply with all FDA safety reporting requirements. Serious Adverse Events Reporting: The principle investigator has the obligation to report all serious adverse events to the University of Texas M. D. Anderson Cancer Center (MDACC) IRB via the Office of Protocol Research in accordance with the timeframes and procedures outlined in "The University of Texas M. D. Anderson Cancer Center Institutional Review Board Policy and also to Celgene and GSK within 24 hours.

IND Annual Reports

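### Section 7.0 gives women of childbearing potential a 28-day post-study contraception minimum, while inclusion criterion 8 requires 6 months after therapy

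*Combined protocol and SAP*

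**What the plan says.** Section 5.0, inclusion criterion 8, applies to women of childbearing potential. A woman must either commit to abstinence or start two forms of contraception together at least 28 days before lenalidomide. She must then "continue it for 6 months after therapy has been completed". The criterion refers to an appendix on fetal exposure, pregnancy testing and birth control.

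Section 7.0, in text addressed directly to the patient, sets out the same choice between two methods and abstinence, with the same 28-day lead-in. It covers the time on study and then continues "for at least 28 days after discontinuation from the study". The table of acceptable methods that follows includes a partner's vasectomy, so this text too is written for women.

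Both statements are in the current protocol body. The supplied text neither reconciles them nor defines when a patient has left the study.

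**The concern.** The two sections differ in length (6 months against 28 days) and in starting point (end of therapy against leaving the study). A woman who leaves the study when therapy ends and stops contraception 28 days later has met Section 7.0 but not the commitment she made at entry.

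The protocol treats fetal exposure as a serious hazard. It makes RevAssist registration mandatory, requires repeated pregnancy tests, and requires 24-hour reporting of suspected exposure. A patient-protection rule of this kind should have one end date. The shorter period also stands in the text worded as an instruction to the patient, which is where a shorter figure is most likely to be followed.

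**Working it through.** The plan gives no figure to reproduce. The check is a comparison of the two rules and calendar arithmetic.

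**Inputs**

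| Item | Inclusion 8 (Section 5.0) | Section 7.0 |
|---|---|---|
| Who | Women of childbearing potential | Women (shown by the methods listed) |
| Starts | At least 28 days before lenalidomide | At least 28 days before lenalidomide |
| Ends | 6 months after therapy | At least 28 days after leaving the study |

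**Step 1: convert to days.** Six consecutive calendar months span 181 to 184 days, depending on the months.

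**Step 2: size of the gap when leaving the study coincides with the end of therapy.** Gap = (6 months in days) − 28.

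- Lower: 181 − 28 = 153 days
- Upper: 184 − 28 = 156 days

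That is about 5 months.

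**Step 3: when the gap closes.** Section 7.0 reaches the 6-month point only if the patient leaves the study at least 153 to 156 days after therapy ends. Between these extremes, the gap shrinks by one day for each day she stays on study after therapy.

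**Step 4: which reading the text favours.** Section 6.0 and Section 7.0 describe what appears to be the same pregnancy-test schedule: weekly for 28 days, then every 28 days (every 14 days if cycles are irregular), with closing tests at the end. Section 6.0 counts the closing tests, at day 28 or at days 14 and 28, from the last lenalidomide dose. Section 7.0 counts the same tests from leaving the study. This suggests that Section 7.0 uses leaving the study to mean stopping treatment, which puts the gap near its maximum and makes inclusion 8 simply the longer rule. It is an inference from parallel wording, not a definition.

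**Step 5: whether 6 months looks deliberate.** Section 9.0 collects serious adverse events for "30 days after the last dose of lenalidomide and for a minimum of 5 half lives (6 months) after the last dose of ofatumumab", so it equates five ofatumumab half-lives with 6 months. The protocol does not give this as the reason for inclusion 8, but the lengths agree.

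**The case against.** The strongest reply is that the two rules do not contradict each other. Section 7.0 sets a floor, nothing in it releases a woman from inclusion 8, and anyone who follows the longer period satisfies both. That stands. A reader might infer that compliance with both is impossible, or that Section 7.0 overrides the entry criterion; the wording supports neither. What remains is the narrower risk that someone works from Section 7.0 alone.

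Second, the appendix cited in Sections 5.0 and 6.0 may state a governing period, and RevAssist compliance is mandatory. Neither the appendix nor the consent form was supplied, so an unresolved safety gap in practice cannot be asserted. This limits the claim to the supplied text. Even a correct appendix would leave two body sections with different minimums.

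Third, post-treatment follow-up might keep patients on study long enough to close the gap. Section 7.0 schedules a liver test 6 months after the last ofatumumab dose, and serious adverse events are collected over the same span. But no section says that either defines being on study. The liver test applies "unless patients have received subsequent treatment for their CLL", and for adverse events, "If a subject does start other therapy, then SAEs will no longer be required to be reported". Section 4.0 also says "it will be possible to continue lenalidomide beyond 24 cycles", so follow-up counted from ofatumumab can be over before lenalidomide stops. These are not contraception rules. They show only that follow-up cannot be relied on to supply the missing months.

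**Conclusion.** The inconsistency is real and should be corrected. Relying on the Section 7.0 minimum alone could leave a woman up to about 5 months (153 to 156 days) short of inclusion 8. That maximum assumes that she leaves the study when therapy ends. The parallel pregnancy-test wording suggests this, but the protocol does not define it. If she stays on study for 153 to 156 days or more after therapy, there is no shortfall.

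A reader might go further and infer that patients were told 28 days or that a fetus was exposed. The documents show neither. Nor should a reader infer that late exposures escape reporting altogether. Expedited pregnancy reporting does apply while the subject "is on lenalidomide and ofatumumab or within 4 weeks after the" last dose of either drug, but a separate sentence has no post-dose limit: "Any suspected fetal exposure to lenalidomide must be reported to Celgene, GSK, MDACC IRB AND ORERM within 24 hours".

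The number of women affected is not given; planned enrolment is 36 patients in total. The two-stage response design, the toxicity monitoring and the analysis are untouched.

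**What to change.** Put one sentence in both inclusion 8 and Section 7.0: *Contraception must continue for at least 6 months after the last dose of lenalidomide or ofatumumab, whichever is later, and not less than 28 days after discontinuation from the study.*

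Counting from the later drug removes doubt about when therapy ends for a woman who continues lenalidomide alone. Keeping the 28-day floor means that neither existing obligation is shortened, however late she leaves the study.

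Before finalising, check that the fetal-exposure appendix and the consent form state the same period.

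The cost is a one-sentence amendment and that check. The downside for patients is a longer contraception period stated in Section 7.0, by up to 153 to 156 days, although inclusion 8 already asks this of women using two methods. There is no effect on sample size, design or analysis.

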6.0 Pretreatment Evaluation

Pretreatment evaluation will include a physical examination including vital signs ECOG/WHO performance status and query for concomitant medications, height and weight and recording of concurrent medications (within 7 days of Day 1).

Clinical laboratory evaluation will include serum chemistry. This will include sodium, potassium, calcium, magnesium, phosphorus, BUN, creatinine, glucose, albumin, total protein, alkaline phosphatase, total bilirubin, ALT, AST, uric acid, and TSH and Beta-2-microglobulin (within 7 days of Day 1).

Hematology: Complete CBC (white blood cell, hemoglobin, platelets and differential) and differential and peripheral blood lymphocyte subset and immunoglobulin levels (within 7 days of registration).

Bone marrow aspiration and biopsy within one month from registration. Bone marrow will be evaluated by flow cytometry for clonality and for IgVH mutation studies (unless known) ZAP-70 expression (unless known), cytogenetic and genomic abnormalities by FISH (unless known).

Electrocardiogram monitoring will be conducted at baseline (within 7 days of Day 1).

Pregnancy Testing and Counseling per the RevAssist® program, assess patient child bearing potential according to the RevAssist® program guidelines outlined below.

Pregnancy tests for females of childbearing potential. A female of childbearing potential (FCBP) is a sexually mature female who: 1) has not undergone a hysterectomy or bilateral oophorectomy; or 2) has not been naturally postmenopausal for at least 24 consecutive months (i.e., has had menses at any time in the preceding 24 consecutive months). Pregnancy tests must occur within 10 – 14 days prior to starting lenalidomide, and again within 24 hours prior to prescribing lenalidomide (prescriptions must be filled within 7 days) and prior to first administration of ofatumumab. FCBP with regular or no menstruation must have a pregnancy test weekly for the first 28 days and then every 28 days while on therapy (including breaks in therapy); at discontinuation of lenalidomide and at Day 28 post the last dose of lenalidomide. Females with irregular menstruation must have a pregnancy test weekly for the first 28 days and then every 14 days while on therapy (including breaks in therapy), at discontinuation of lenalidomide and at Day 14 and Day 28 post the last dose of lenalidomide (see Appendix: Risks of Fetal Exposure, Pregnancy Testing Guidelines and Acceptable Birth Control Methods).

Lenalidomide must be prescribed through and in compliance with the RevAssist® program of Celgene Corporation. Prescriptions must be filled within 7 days. Consideration should be given to prescribing lenalidomide 5 to 7 days in advance of lenalidomide administration of each cycle to allow time for required patient and prescriber surveys, and drug shipment to patient. Any unused Revlimid® (lenalidomide) should be returned to the patient for disposition in accordance with the RevAssist® program.

